1. PURPOSE OF THE STUDY

a. Brief Summary

Continuous deep brain stimulation (cDBS) is an established therapy for the major motor signs in Parkinson's disease. Currently, cDBS is limited to "open-loop" stimulation, without real-time adjustment to the patient's state of activity, fluctuations and types of motor symptoms, medication dosages, or neural markers of the disease. The purpose of this study is to determine if an adaptive DBS system, responding to patient specific, clinically relevant neural or kinematic feedback, is more effective than continuous DBS on the motor Unified Parkinson's Disease Rating Scale (UPDRS III) and specific phenotypic measures in Parkinson's Disease.

b. Objectives

- 1). Determine the efficiency and effectiveness on PD signs of adaptive DBS (aDBS), triggered by patient-specific resting state neural activity, compared to continuous DBS (cDBS) using the UPDRS III and validated, high-resolution kinematic metrics of tremor, bradykinesia and freezing of gait (FOG).
- 2). Determine whether aDBS using a kinematic classifier pertinent to the patient specific phenotype is more efficient and/or effective on PD symptoms than aDBS using the using the patient's specific resting state neural classifier and/or cDBS.
- 3). Determine whether aDBS is more efficient and effective than cDBS in the optimized on medication state after six months of cDBS. We believe that the results of these experiments will make it possible for DBS to realize its full potential: a new generation of context-dependent, continuously adaptive DBS devices will have the ability to sense and modulate brain signals that are correlated to abnormal movement and will provide DBS therapy in different locations based on motor phenotype and state of activity.

c. Rationale for Research in Humans

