The Nexus D and Nexus E systems are a newly developed technology allowing for bi-directional communication of information between the Activa® PC+S and a portable computer (PC). The PC will use real time neural and kinematic data to develop classifiers of the behavioral states of rest, tremor, and bradykinesia in PD. The investigator team will develop a series of algorithms (control policies) on the PC, which will inform the Activa® PC+S to turn ON or OFF (at a preset, safe and therapeutic setting) based on the kinematic or neural classifiers of PD. Using this established neural interface for the first time in human PD subjects, we will develop optimal patient-specific customized classifier and control policy algorithms. This will drive the future creation of closed-loop neuromodulation devices, embedding and automating sensing and stimulating platforms.

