SA1. Resting state neural: ON and OFF triggers when the beta band power $> 50\%$ and $< 25\%$ respectively of the resting state beta power differential (beta power OFF – ON therapeutic DBS). SA2. Kinematic, tremor/bradykinesia: ON and OFF triggers when rectified tremor amplitude/root mean square angular velocity (Vrms) of WFE $> 50\%$ or $< 25\%$ of tremor/Vrms differential (OFF – ON therapeutic DBS) respectively.

Specific Aim 1b and 2b (SA1b, SA2b): Outcomes will be measured after 30 minutes of aDBS or cDBS. For neural and tremor aDBS, the Activa® PC+S will be updated in real time. For bradykinesia aDBS, the Activa® PC+S will be updated with the Vrms from 10 second epochs of WFE that the PD subject will perform every 2 minutes during the 30 minute trial. At the six month visit the subject will come in on medication on stimulation and SA1 and SA2 will be repeated in the then optimized on medication state. The control policy algorithms will be adjusted as necessary to adapt to this state (Specific aim 3, SA3) At the 1, 3, 6, 9 and 12 month visits subjects will come in off medication and on stimulation and will repeat quantitative assessment of motor function. This may include quantitative digitography (QDG), quantitative range of motion analysis (Motus, LG G Watch, APDM System), tremorography, surface electromyography (EMG), and computerized dynamic posturography and UPDRS III. The subject will perform these assessments in the on clinical stimulation state and will repeat all or a subset of these tests in the off stimulation state. Subjects may continue these motor tests after the 12 month visit during their regularly scheduled clinic visits. Most often, this is every 3 months, however, patients may come in more or less often, depending on their clinical schedules.

For subjects already enrolled in eprotocol 25916:

Subjects who have been implanted with the Activa PC+S Neurostimulator system and who are enrolled or who have completed the Brain Radio initial study may be asked to consent to Nexus study. They will be asked to come in for additional visits (may be at follow-up if still enrolled or an additional study session.) These participants may complete the specific aims 1,2,3 listed in above protocol in addition to collecting data recordings with Nexus-D and Nexus-E systems.

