9. RISKS

a. Potential Risks

i. Investigational devices

The investigational DBS device (Activa PC+S model 37604) is based on the FDA approved commercial DBS device (Model 37601 Activa PC) but adds the functionality of bioelectrical data recording (sensing). Activa PC and Activa PC+S share the same therapy and form factor and there are no new tissue contacting materials in Activa PC+S. Therefore the risks of the Activa PC+S should be similar to Activa PC. We don't anticipate that there will be any additional risks associated with using this device.

The risks of implanting the FDA approved device (Activa PC) are minimal but include risks at surgery of local bleeding, skin contusion or infection, tenderness at the site of implantation, device failure, discomfort after device placement in subcutaneous tissue, or due to local current spread if there is a break in the lead or connections.

The Nexus-E investigational research tool is only FDA approved for use in studies such as this one and is not commercially available. The Nexus E-System will only be used during study visits and will only be able to make changes to stimulation within the preset safety constraints set by a clinician. The Nexus-E System does not allow the clinician or pre-written algorithms to change the stimulation configuration beyond those pre-set safety limits. Potential issues that could occur while using the Nexus-E system may include device malfunction or premature battery drainage of the DBS device.

The tactile stimulator, which uses C-MF Tactors, is being used for an off-label use as treatment for Parkinson's disease. The device gently vibrates the fingertips. We suggest that this is a non-significant risk device. No official statistics are available on its safety. The only theoretical anticipated risk might be worsening of Parkinson's symptoms. We will be vigilant for this unlikely possibility. We have tested this device in another protocol for safety and tolerability (35238), and we have not had any reported discomfort from the vibratory stimulation.

Risks associated with using Google Glasses during forward walking tasks are minimal but may include losing balance while watching videos on display.

ii. Investigational drugs

NA

iii. Commercially available drugs, biologics, reagents or chemicals

NA

iv. Procedures

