### **Analysis of primary outcome**

The number and percentage of occurrences of treatment-related adverse events (AE) will be reported for each treatment arm of continuous DBS (cDBS), adaptive DBS (aDBS) and off DBS.

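### The primary safety table counts only treatment-related AEs and states no exposure, so the off-DBS row is low largely by construction and the rows are hard to compare

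*SAP*

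**What the plan says.** The SAP section Analysis of primary outcome is a single sentence. It promises counts and percentages of "treatment-related adverse events (AE) will be reported for each treatment arm of continuous DBS (cDBS), adaptive DBS (aDBS) and off DBS". It contains no test, margin, interval, observation window or stated denominator. The protocol's Study Endpoint(s) entry (2.g) reads NA, so nothing there widens or replaces it.

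The conditions differ in what is delivered. Off DBS gives no stimulation. In aDBS a computer runs control algorithms "which will inform the Activa® PC+S to turn ON or OFF" (Protocol 1.c), so stimulation may be absent for part of an aDBS trial.

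On exposure, Protocol 2.a says: "Outcomes will be measured after 30 minutes of aDBS or cDBS". For the later on-medication stage it says: "At the six month visit the subject will come in on medication on stimulation and SA1 and SA2 will be repeated". Protocol 9.a.i adds: "The Nexus E-System will only be used during study visits". Active participation, however, is 2 to 5 years (Protocol 8.m), and Objective 3 uses cDBS for six months of ongoing therapy. No duration is given for the off-DBS condition.

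The single aDBS entry covers three control schemes. Protocol 2.a states: "For neural and tremor aDBS, the Activa® PC+S will be updated in real time". Bradykinesia aDBS instead relies on "10 second epochs of WFE that the PD subject will perform every 2 minutes during the 30 minute trial".

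**The concern.** A filter on relatedness can be applied evenly only if an event has a similar chance of being called related in each row. Off DBS fails that condition on the face of it. With no current delivered, an event can hardly be a stimulation effect, so it counts only if treatment is read to include the implant, or the act of withdrawing stimulation. A low off-DBS figure would then reflect the definition at least as much as the patients' experience.

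An ON/OFF controller also carries a risk of its own: harm while stimulation is withheld. Whether such an event is related (therapy was withheld) or unrelated (no stimulation was running) is left open. If it is called unrelated, the table omits the kind of harm most specific to the new system.

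Finally, an AE percentage cannot be read without knowing over what time and among whom the events were counted. At stake is the interpretability of the only analysis that the SAP labels primary.

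**Working it through.** **1. The plan's own figures.** No figure in either document bears on the AE outcome. The one computed design figure, 9 subjects in the SAP's Power analysis, concerns freezing counts. It reproduces: the difference is 0.65 × 4.9 = 3.185. Taking the SD of the differences as 2.47 (an assumption), a two-sided paired t-test at 0.05 needs n = 7 (power 0.81), and 7 / 0.87 = 8.05, which rounds up to 9. It neither helps nor harms the point here.

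**2. Is the filter softened elsewhere?** I looked for four things.

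| Needed | Found |
|---|---|
| Definition of treatment-related, or which treatment is meant | None in either document |
| Who judges relatedness, and whether blinded to condition | Not stated |
| A planned table of all AEs | None; Protocol 9.e has monitors document any AE and report to the IRB, which is oversight |
| Window and denominator | Not stated |

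**3. Effect of the filter on the off-DBS row (assumed rates).** Shown rate = all-cause rate × share called related. Let the all-cause rate be 20% in every condition, so there is no true difference. With none of the off-DBS events called related, the off row is 20% × 0 = 0%. On stimulation:

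- share 25%: 20% × 0.25 = 5%
- share 50%: 20% × 0.50 = 10%
- share 75%: 20% × 0.75 = 15%

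The apparent excess on DBS is 5 to 15 percentage points, all of it produced by attribution. If a few off-DBS events were called related, say 10% of them, the off row would be 20% × 0.10 = 2% and the excess 3 to 13 points.

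**4. Exposure.** Two readings of the cDBS row are open.

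- *Matched sessions.* Protocol 2.a gives 30 minutes of aDBS or cDBS, so one trial of each has equal exposure.
- *All time on cDBS.* Chronic stimulation continues between visits during participation of 2 to 5 years, while the Nexus-E system that drives aDBS is confined to visits. The row would then set years beside 30-minute trials.

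The SAP does not choose between them. Even on the first reading a denominator is needed, since a patient may have more than one aDBS trial. Assume 5% per trial, independent trials, and each patient counted once. One cDBS trial gives 5%; two aDBS trials give 1 − 0.95² = 9.8%; three give 1 − 0.95³ = 14.3%. Equal risk per trial then looks like excess risk on aDBS.

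**5. Pooling of controllers (a side issue).** With equal numbers of trials, a 10%, 20% or 30% rate in one controller and 0% in the other two appears in a single row as 10/3 = 3.3%, 20/3 = 6.7% or 30/3 = 10%. These rates are also assumed.

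**The case against.** The best reply is that much of this is inferred. No text applies a different attribution rule to each condition, and the SAP itself calls off DBS a treatment arm, so its authors may have meant relatedness to include the implant or stimulation withdrawal. This stands for cDBS against aDBS: a reader might infer that the plan treats those two unequally, and the documents do not show it. It is weaker for off DBS, where the absence of stimulation is a fact and only an unstated, broader definition would rescue the row.

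Second, the table is descriptive. That stands: no type I error or power is affected. But the table is the whole primary result, so what enters it still matters.

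Third, all AEs are watched anyway. Monitors document them, adverse effects prompt immediate IRB reports, and suicidality is screened at study visits. This shows that AEs are not ignored, and a reader should not infer that they go uncollected. It does not amount to a planned analysis by condition.

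Fourth, pooling the controllers is defensible. Objective 2 asks whether "aDBS using a kinematic classifier pertinent to the patient specific phenotype is more efficient and/or effective on PD symptoms", which concerns effect rather than safety; stimulation stays within limits fixed by a clinician; and a patient may receive only the neural and one kinematic controller. This stands, so separate rows are an optional addition.

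**Conclusion.** The point holds as a cheap improvement to the primary table, not as an error that invalidates the trial. Two parts are firm: only related AEs are counted, in a table that includes a condition without stimulation, and no window or denominator is given. The loss of OFF-phase events in aDBS is a possibility that follows from the missing definition, not a stated rule.

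The size cannot be estimated, because neither document gives AE rates. The 5% to 15% against 0% contrast assumes a 20% all-cause rate in every condition, 25% to 75% attribution on stimulation and none off it. It shows the mechanism and does not forecast a result.

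A reader might go further and conclude that aDBS is only a minute share of the observed time and that the comparison is therefore meaningless. The documents do not support this: the protocol also describes matched 30-minute trials, and total aDBS time per patient is not fixed, since other tasks and additional visits are allowed. The defect is that the SAP leaves the choice open. Likewise, the small number of patients limits precision under any attribution rule and is not evidence for this point.

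**What to change.** Rewrite the SAP's Analysis of primary outcome as follows.

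- Tabulate all AEs with onset during supervised test sessions, whatever their attribution, by stimulation condition at onset: cDBS, aDBS, off DBS.
- Give the number of patients and the session time exposed for each condition.
- Show treatment-related AEs as a second column. Define related to include effects of stimulation being withheld by the controller.
- List AEs arising outside test sessions separately.
- Optionally, add descriptive neural, tremor and bradykinesia rows beneath the pooled aDBS row.

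The cost is SAP wording plus two items recorded at the visit: condition at AE onset and session time in each condition. No extra patients or visits are needed. The stimulation-state epochs in the SAP's Neural Signal Analysis should not be used for exposure: sections with artifact are removed, so they would understate it.

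There are downsides. More events will be displayed, counts per row will be small (smaller still by controller), and an event just after a switch may belong to the preceding condition. The last can be met by also noting the preceding condition for such events.

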### **Analysis of secondary outcomes**

For Alpha/beta power and Sample Entropy (SampEn): Alpha/beta power varied across subjects sometimes by orders of magnitudes. Relative alpha and beta power was calculated by dividing the summed absolute alpha or beta power by the summed power in the 40- 70 Hz band during the resting state, and allowed comparison across subjects, whose raw signal magnitude can vary by one or two orders of magnitude, see Supplementary information. The FW task was analyzed by excluding the turning periods at the end of the 10 m of straight walking. As a result, each FW task had 4 trials.

Similarly, as the TBC task had four trials, it was also analyzed as four separate time periods for each patient. The SIP task had one trial per patient. Asymmetry and arrhythmicity were assessed individually using a linear mixed effect model in Freezers and Non-Freezers during FW, while a one-way ANOVA was used in SIP. A one way ANOVA and a Kruskal-Wallis test by ranks was also used to determine if alpha or beta power and SampEn changed significantly between Freezers and Non-Freezers in SIP, while a linear mixed effects model was used for both TBC and FW, in order to account for the four trials. Freezer or Non-Freezer type was a fixed effect and a factor variable with 2 levels (Freezer and Non-Freezer). Subject STN was a random effect, and a random intercept was used in the model. Residuals were assessed for homoscedasticity and normality, and all statistical assumptions were met.

To compare arrhythmicity, asymmetry, or stride time between groups, a one-way ANOVA was used. Paired t-tests were used to compare the effects of different stimulation frequencies on arrhythmicity, asymmetry, and stride time within each group for each task. Post hoc analyses were completed to compare between stimulation conditions. All statistical testing was performed in SigmaPlot (Systat Software, San Jose, CA) using two-tailed tests with significance levels of  $P < .05$ .

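### For gait measures in the FW and TBC tasks, the SAP names overlapping or trial-blind tests and does not state the unit of analysis for the one-way ANOVA and paired t-tests.

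*SAP*

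**What the plan says.** All the wording at issue is in the SAP, Analysis of secondary outcomes.

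- **Trials per task.** For FW: "As a result, each FW task had 4 trials". For TBC: "Similarly, as the TBC task had four trials, it was also analyzed as four separate time periods for each patient". For stepping in place: "The SIP task had one trial per patient".
- **Neural measures.** For alpha/beta power and sample entropy, SIP gets a one-way ANOVA and a Kruskal-Wallis test, "while a linear mixed effects model was used for both TBC and FW, in order to account for the four trials". On the random part of the model: "Subject STN was a random effect, and a random intercept was used in the model". Its one stated fixed effect is Freezer versus Non-Freezer.
- **Gait measures, first statement.** "Asymmetry and arrhythmicity were assessed individually using a linear mixed effect model in Freezers and Non-Freezers during FW", with a one-way ANOVA for the same measures in SIP.
- **Gait measures, second statement, next paragraph.** "To compare arrhythmicity, asymmetry, or stride time between groups, a one-way ANOVA was used". No task is named.
- **Stimulation contrasts.** "Paired t-tests were used to compare the effects of different stimulation frequencies on arrhythmicity, asymmetry, and stride time within each group for each task".

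Tests are two-sided at the 5% level. The SAP gives no within-patient correlation, no Freezer/Non-Freezer split, and no statement of whether the ANOVA and t-tests run on trials or on one value per patient.

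**The concern.** The SAP recognises that four trials from one patient are not four independent observations, and it uses a mixed model for the neural measures for that reason. The same four trials yield the gait measures, but there the protection is written only for asymmetry and arrhythmicity in FW, and the next paragraph appears to override it.

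Two things follow. For those two FW measures an analyst could follow either statement and still be within the plan. For the remaining gait comparisons in FW and TBC, the named tests have no term for repeated trials, so their validity depends on a choice the SAP leaves open. If trials enter as rows, the sample looks four times larger than it is and the P values for the group comparison are too small.

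**Working it through.** **Step 1. Between-group method by measure and task, as written.**

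| Measure | FW (4 trials) | TBC (4 trials) | SIP (1 trial) |
|---|---|---|---|
| Asymmetry, arrhythmicity | mixed model and ANOVA | ANOVA only | ANOVA |
| Stride time | ANOVA only | ANOVA only | ANOVA |
| Alpha/beta power, sample entropy | mixed model | mixed model | ANOVA and Kruskal-Wallis |

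The conflict between two methods is confined to the first cell. In the other FW and TBC gait cells the gap is a missing rule for the four trials. SIP has no repeated-trial problem.

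**Step 2. Inputs for the size.** From the SAP: m = 4 trials per patient, two-sided 5% level (critical value 1.96). Not in the documents, so assumed: the ICC, shown over a range, and the group sizes. Protocol section 8a gives only an upper limit of 34 patients; simulations used 5+5, 8+6, 9+9 and 17+17.

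**Step 3. ANOVA on trial rows, large-sample formula.** The design effect is DE = 1 + (m - 1) × ICC = 1 + 3 × ICC. The true false-positive rate is 2 × [1 - Φ(1.96/√DE)]. At ICC = 0, DE = 1 and the rate is 5.0%, which returns the SAP's nominal level.

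| ICC | DE | 1.96/√DE | Formula | Simulated, range over group sizes |
|---|---|---|---|---|
| 0.1 | 1.30 | 1.72 | 8.6% | 8.5-8.9% |
| 0.3 | 1.90 | 1.42 | 15.5% | 15.6-16.5% |
| 0.5 | 2.50 | 1.24 | 21.5% | 22.0-23.2% |
| 0.95 | 3.85 | 1.00 | 31.8% | not run at 0.95 |

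The simulations (20,000 datasets per setting, no true difference) run slightly above the formula when groups are small. Near the top of the range they gave 31.8-35.8% at ICC 0.9 and 33.5-37.8% at 0.99.

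**Step 4. ANOVA on one mean per patient.** Same simulated data: 4.8-5.2% at every ICC and group size.

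**Step 5. Paired t-tests on trial pairs.** Taking differences between conditions cancels a patient's overall level. The four differences from one patient stay correlated only if the stimulation effect itself differs between patients. Simulated with 5, 9 and 17 patients:

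| ICC of the differences | Trial pairs | Patient means |
|---|---|---|
| 0 | 4.8-5.3% | 4.8-5.1% |
| 0.2 | 11.9-12.6% | 5.0-5.3% |
| 0.5 | 21.8-22.8% | 4.8-5.0% |

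The zero row holds even when 50% or 80% of the variance lies between patients. A high trial ICC alone does not inflate this test.

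The mixed model was not simulated. The 5% results above are for patient means.

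**The case against.** The strongest reply is that nothing in the SAP says trial rows enter the ANOVA or the t-tests. Averaged to one value per patient, both tests are valid. The authors plainly know the issue, since they use a mixed model where there are four trials and give SIP the ANOVA. On this view the later ANOVA sentence restates SIP or presumes patient means. With balanced data, an ANOVA on patient means and a patient-level mixed model should also largely agree, so having two named tests would do little harm.

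Part of this stands. A reader might infer that the planned tests do run at 15-32%; the documents do not support that, because the inflation needs both trial-row entry and a substantial ICC. The charitable readings are not written down, however. A SIP-only reading largely repeats what the previous paragraph says and sits beside a sentence covering every task. Averaging is never mentioned, and the TBC sentence about separate time periods points towards trial-level data.

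Three further replies also stand. The ANOVA range cannot be carried over to the paired t-tests (Step 5). The ANOVA sentence covers three measures, not every TBC gait measure: the SAP's Kinematic Analysis paragraph also lists gait speed, swing duration and freezing episodes. And the planned mixed model has a Subject STN intercept and no stimulation term, so applying it to stimulation contrasts is an extension of the plan.

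**Conclusion.** The concern holds as a conflict of stated methods for FW asymmetry and arrhythmicity, and as an unstated unit of analysis for the ANOVA and paired t-tests in FW and TBC.

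The possible size is conditional. For the ANOVA on trial rows treated as independent, it is about 9% at ICC 0.1, rising to about 32% at 0.95, against a nominal 5%. For the paired t-tests it is about 12% and 22% at an ICC of the differences of 0.2 and 0.5, and about 5% if the stimulation effect does not vary between patients. The ICCs and group sizes are assumptions. With one value per patient there is no inflation.

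A reader might also infer that the paired t-tests must be dropped, or that the trial's main result is at risk. Neither follows. Paired t-tests on patient means are valid, and the SAP's primary outcome is a descriptive tabulation of adverse events. The affected results are secondary gait comparisons.

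**What to change.** 1. Limit the one-way ANOVA sentence to SIP.
2. For arrhythmicity, asymmetry and stride time in FW and TBC, name one between-group method: a linear mixed model with Freezer type as a fixed effect and a patient-level random intercept. The intercept has to be specified for the patient, since the one now written is for Subject STN.
3. For stimulation contrasts in FW and TBC, choose one option in advance and write it down. Either run the paired t-tests on each patient's mean over the four trials, or use a mixed model with stimulation condition as a fixed effect and a patient-by-condition random term.
4. State the unit of analysis for each test.

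The cost is SAP wording and a small extension of a model type already in the plan, with no new data. P values may be less favourable than under a trial-row analysis; if patient means were intended all along, little should change.

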### Power analysis

Thirteen/fifteen (~87%) freezers had at least one freezing episode during the SIP task (mean number of freezes = 4.9, STD=+/- 2.47). Previous studies found an average of 66% improvement in freezing metrics between ineffective and effective stimulation conditions. A power analysis (paired t-test) using the mean number of freezes with ineffective/NO DBS (4.9, STD +/- 2.47, from above) and a 65% improvement from effective stimulation shows that the largest sample size required for significant outcomes is 9 subjects with freezing during SIP (alpha=0.05, power=0.8, assuming only 87% of patients will freeze during tasks).

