### Comparison of characteristics at baseline

Student's t-tests were used to compare age, disease duration, pre-op and post-op Unified Parkinson's disease Rating Scale (UPDRS) between the Freezer and Non-Freezer groups.

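### The Freezer versus Non-Freezer ANOVAs pool the two groups' variances, so their true error rate can lie above or below 5%, depending on a group split and spread that the plan does not state

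*SAP*

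**What the plan says.** The SAP's section on secondary outcomes compares Freezers with Non-Freezers in three ways.

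- **Gait.** "To compare arrhythmicity, asymmetry, or stride time between groups, a one-way ANOVA was used". The sentence names no task. Just before it, the SAP says: "Asymmetry and arrhythmicity were assessed individually using a linear mixed effect model in Freezers and Non-Freezers during FW, while a one-way ANOVA was used", the ANOVA being for SIP.
- **Neural measures, stepping task.** The SAP writes: "A one way ANOVA and a Kruskal-Wallis test by ranks was also used to determine if alpha or beta power and SampEn changed significantly". The contrast is again of the two groups. The rank test is named here and not for the gait measures.
- **Neural measures in the FW and TBC tasks.** A linear mixed model with a two-level Freezer factor. Its description ends: "Residuals were assessed for homoscedasticity and normality, and all statistical assumptions were met".

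All tests are "two-tailed tests with significance levels of" P < .05. For baseline characteristics the SAP says "Student's t-tests were used to compare age, disease duration" and UPDRS between the same two groups. No unequal-variance test is named anywhere.

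Neither document gives the number of Freezers or Non-Freezers, or an SD by group for any variable in these tests. The one SD is for freeze counts in freezers, in the SAP's power analysis: "mean number of freezes = 4.9, STD=+/- 2.47".

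**The concern.** A pooled test estimates one common variance, and the larger group dominates that estimate. If the smaller group is the more variable one, the standard error comes out too small and the test rejects too often. If the larger group is the more variable one, the standard error is too large and real differences are missed.

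Neither safeguard is secured here. The protocol's eligibility criteria (section 8h) do not mention freezing, so the split falls as recruitment happens to produce it. Unequal spread is a reasonable expectation for some of the measures. The protocol (section 2a) says SIP separates freezers from non-freezers with 93% sensitivity and 87% specificity, and it links stepping asymmetry and rhythmicity to the mechanisms of freezing. Patients who freeze to differing degrees may well vary more on these measures than patients who do not freeze.

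At stake is whether a P value below .05 for a gait or neural difference between the groups means what it says.

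**Working it through.** **1. The plan's own figure.** The only computed sample size is the 9 subjects in the SAP's power analysis. The effect is 0.65 × 4.9 = 3.185 freezes. I assume an SD of differences of 2.47, which corresponds to a within-patient correlation of 0.5. Then d = 3.185 / 2.47 = 1.289. A two-sided paired t-test at 5% needs n = 7 (power 0.81), and 7 / 0.87 = 8.05, rounded up to 9. The figure reproduces. It is the size for a within-patient comparison of stimulation conditions and says nothing about the Freezer to Non-Freezer split.

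**2. Inputs for the between-group tests.**
- Alpha 0.05, two-sided: SAP, secondary outcomes.
- Total patients: up to 34 (protocol 8a) or 30 (protocol 9d).
- Split: not given, so a range is shown.
- SD ratio, Freezer to Non-Freezer: not given, so 1.5, 2 and 3 are assumed.

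**3. Why the split matters.** With two groups, the ANOVA F equals t², where t divides the mean difference by √[s²(1/n_F + 1/n_N)] and s² = [(n_F − 1)s_F² + (n_N − 1)s_N²] / (n_F + n_N − 2). The true variance of the difference is σ_F²/n_F + σ_N²/n_N. With σ_F = 2 and σ_N = 1:

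| Freezers : Non-Freezers | True variance | Average variance the pooled test uses | True / used |
|---|---|---|---|
| 17:17 | 4/17 + 1/17 = 0.294 | 2.5 × (1/17 + 1/17) = 0.294 | 1.00 |
| 13:21 | 4/13 + 1/21 = 0.355 | 2.125 × (1/13 + 1/21) = 0.265 | 1.34 |
| 9:25 | 4/9 + 1/25 = 0.484 | 1.75 × (1/9 + 1/25) = 0.264 | 1.83 |
| 25:9 | 4/25 + 1/9 = 0.271 | 3.25 × (1/25 + 1/9) = 0.491 | 0.55 |

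**4. Actual error rate at nominal 5%.** Simulation with normal data and equal means, 100,000 replicates per cell:

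| Freezers : Non-Freezers | Pooled, SD ratio 1.5 | Pooled, 2 | Pooled, 3 | Welch, all three ratios |
|---|---|---|---|---|
| 17:17 | 5.0% | 5.2% | 5.5% | 4.9-5.0% |
| 13:21 | 7.3% | 9.2% | 11.3% | 4.9-5.2% |
| 10:20 | 8.5% | 11.4% | 14.6% | 5.1% |
| 9:25 | 10.3% | 14.8% | 20.2% | 5.1-5.2% |
| 21:13 | 3.4% | 2.7% | 2.1% | 4.9-5.1% |
| 25:9 | 2.0% | 1.0% | 0.5% | 4.9-5.0% |

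Over all splits run, including smaller samples such as 5:10, Welch's test stayed between 4.7% and 5.6%.

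**5. Would a variance check or the rank test protect?** At 9:25 with an SD ratio of 2, a Levene test (median-centred) detects the difference about 50% of the time. In the data sets that pass it, the pooled test still rejects about 17% of the time. Kruskal-Wallis at 9:25 rejects in about 8%, 10% and 13% of data sets at SD ratios 1.5, 2 and 3.

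**The case against.** - **The SAP says the assumption was checked and met.** This is the strongest reply. The sentence says all assumptions, and its paragraph also describes the SIP ANOVAs, so it may be meant to cover those. It follows directly on the mixed-model description, and the general gait ANOVA comes only in the next paragraph. Its scope is therefore unclear. It reports a result, with no rule for the case where the check fails. Step 5 shows that passing such a check gives limited reassurance at these sizes.
- **The inputs are not in the documents.** This stands. The SD of 2.47 is for freeze counts, which none of these ANOVAs test, and it gives no variance ratio for gait. For alpha/beta power and entropy the documents suggest no reason for unequal spread. Those comparisons are included only because they use the same test.
- **Equal means with very unequal spread is an unlikely state.** Freezing that widens the spread may also shift the mean. That is fair for a pure false positive. The error in the pooled standard error does not depend on the means, however, so confidence intervals and power are affected too.
- **The stakes are modest.** This stands. The SAP's primary outcome is a descriptive count of adverse events, and the protocol's objectives compare stimulation modes rather than these groups.

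A reader might also infer that the SAP plans 9 Freezers, leaving 21 to 25 Non-Freezers out of 30 to 34. It does not: step 1 shows that the 9 belongs to a paired comparison.

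**Conclusion.** The point holds as a conditional one. The two-group ANOVAs pool variances, nothing in the design makes that safe, and the error rate can be off in either direction. Over assumed SD ratios of 1.5 to 3, it is essentially right with equal groups and moderately high at 13:21. It reaches two to four times nominal at 9:25 and falls well below nominal if Freezers are the clear majority.

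Three stronger readings are tempting but not supported:
- **That the error is 10-20% as the plan stands.** At an SD ratio of 2 this needs Freezers outnumbered by about 2:1 or more. The documents give neither the split nor the ratio.
- **That the baseline t-tests are affected in the same way.** The argument about spread concerns freezing-related gait. It does not carry over to age, disease duration or UPDRS, which are descriptive comparisons.
- **That the mixed models need separate variances by group.** No calculation here supports that, and with few Freezers such variances could be poorly estimated.

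This is worth changing in a secondary analysis. It does not threaten the primary result.

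**What to change.** In the SAP's section on secondary outcomes, replace the one-way ANOVA with Welch's test for every two-group Freezer versus Non-Freezer comparison that now uses it. Specify it from the start, not after a variance pre-test. Report each difference with its Welch 95% confidence interval, together with the group sizes and SDs. State which analyses the homoscedasticity sentence covers. Welch's test could also replace Student's t-test at baseline, for consistency only.

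**Cost.** If the variances are in fact equal, about 1 to 4 points of power are lost. For a difference of about 1.0 to 1.1 SD, power goes from about 79% to 76% at 9:25 and from about 80% to 79% at 12:22. Otherwise the change is one of wording. Much of the section is in the past tense, so if analyses have already been run they would need repeating. Welch's test needs only each group's mean, SD and size.

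**Limit.** Welch's test does not cure skewness. With lognormal data, an SD ratio of about 2 and a 9:25 split, it rejects in about 7-9% of data sets, against about 15% for the pooled test.
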